
Domain Secondary Outcome:
	
 
1. Mortality at other endpoints (ICU/hospital discharge, 30 days and 6 months)
 
2. Hospital length of stay
 
3. Duration of NIV
 
4. Duration of supplemental oxygen use
 
5. Ordinal scale of daily respiratory support
 
6. Need for ECLS
 
7. Duration of ECLS (for those that require ECLS)
 
8. Ventilator-free days (VFDs) censored at day 30
 
9. Health-related quality of life at 6 months (measured with EQ-5D)
 
10. Complications from Corticosteroids: 
 
a. Hyponatremia (serum sodium > 150 mmol/L)
 
b. Hyperglycemia (requiring new insulin or increase in insulin by >30% from initial/baseline dose)
 
c. Delirium
 
d. Clinically important GI bleeding (requiring endoscopy or RBC transfusion)
 
e. Nosocomial infection
 
f. Neuromuscular weakness
 
 
 

Domain Design:
	
A phase III, interventional, open-label, randomized, multi-site study

Duration:
	
2.5 years of accrual and 6 months follow-up for a total study duration of approximately 3 years.

Planned Total Sample Size:
	
The Bayesian approach does not require a fixed sample size as the trial will continue enrolling until a statistical trigger is met (see section Sample Size for additional details). It is estimated that a maximum of 2000 patients will be enrolled in each cohort at 30 to 40 sites.

Inclusion/Exclusion Criteria:	
Patients will be eligible for enrolment in this domain if they meet the PRACTICAL platform eligibility criteria and the criteria specific to either cohort in the CORT-E domain.
 
PRACTICAL Inclusion Criteria
 
1) Acute hypoxemic respiratory failure meeting all of the following criteria;
 

a) New or worsening respiratory symptoms developing within 2 weeks prior to the onset of need for oxygen or respiratory support

b) Receiving any of the following types of oxygen or respiratory support for at least 4 hours prior to the time of randomization; supplemental oxygen at 10 L/min or higher, high flow nasal oxygen (at any flow rate),

--------------------------------------	--

[figure not shown]

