**Study Assessment Schema**

Required Investigations*	Baseline	Daily**	D3	D7	D28 or ICU DC 	D60 	6 Months 
Window	Within 72 hours prior to randomization	N/A	N/A	N/A	N/A	+10 days	+/- 14 days
Consent  & Randomization	X						
Demographics 	X						
Medical History 	X						
Vitals 	X	X					
Hemodynamics 	X	X					
Hematology 	X	X					
Biochemistry 	X	X					
Arterial Blood Gases (ABG) 	X	X					
Study Drug Administration	Refer to the 'TRIAL INTERVENTIONS' section for details related to each cohort						
Optional: Blood Sample Collection	X		X	X	X		
Mechanical Ventilation Data		X					
Readiness to Wean	X	X					
Spontaneous Breathing Trial		X 					
EQ-5D-5L							X

Glasgow Coma Scale and Sofa Score	X	X					
Vital Status						X	X
Serious Adverse Events		X 					
Concomitant Medications		X					

 Consent should be done prior to any baseline assessments and according to site institutional timelines. Site should follow their institutional guidelines for consenting window (timeframe for prior to enrollment/protocol treatment). Please refer to section “Patient population, eligibility and enrollment”.

 Demographics include age, gender, height, and weight.

 Hospital admission (date/time), ICU admission (date/time), APACHE IV, Charlson Comorbidity Index, COVID-19 infection status

 Vitals include temperature, heart rate, respiratory rate, and blood pressure.

 Hemodynamics include BP, PCWP, SvO2

 If multiple time points for baseline data are available within the time point window, values closest to randomization should be entered.

 Hematology reporting on Hg, WBCs, and platelets.

 Biochemistry will include reporting the following values: sodium, glucose, creatinine, albumin, bilirubin, potassium, bicarbonate.

 ABG testing will include the following parameters: pH, PaCO2, HCO3, SaO2, lactate, hemoglobin.

 Spontaneous breathing trials will be conducted only when patient is deemed ready for weaning and per standard of care and/or institutional guidelines.

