### Sample Size

The Bayesian approach does not require a fixed sample size as the trial will continue enrolling until any of the following statistical triggers are met:

- A. Superiority ( $\geq 99\%$  posterior probability of  $OR < 1$  for 60-day mortality) or
- B. Inferiority ( $\geq 99\%$  posterior probability of  $OR > 1$  for 60-day mortality) or
- C. Equivalence ( $\geq 90\%$  posterior probability of  $0.8 < OR < 1.2$  for 60-day mortality).

[figure not shown]
These triggers will be evaluated separately in Early Cohort and Extended Cohort with decisions for stopping made separately in each Cohort. To estimate potential sample size requirements, ensure adequate statistical power and compute the risk of incorrectly concluding superiority in the absence of any benefit (Type I error), we conducted statistical simulations for a range of plausible scenarios for treatment effects ( $OR = 0.75, 0.8, 0.9, 1.0$ ). These scenarios were based on our previous meta-analysis that demonstrated an  $OR$  of  $0.73-0.79$  for corticosteroids in reducing mortality in COVID or non-COVID AHRF, depending on baseline risk, estimated from a large Toronto registry (<https://criticalcare.utoronto.ca/icore>). We adjusted for differences in baseline risk using Bayesian logistic regression. Our simulations suggest a maximum expected sample size of approximately 2000 patients for each of Early Cohort and Extended Cohort (simulations were extremely similar for both domains) would be suitable. This provides a power of 94% for an  $OR$  of 0.75, the most plausible  $OR$  given the previous meta-analysis, 0% probability of concluding inferiority when  $OR > 1$  and a Type I error under the null scenario ( $OR = 1.0$ ) of below 5% at any time during enrolment.

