### **Analyses**

Any deviation from the original statistical plan will be described in the final report.

[figure not shown]

All analyses, interim and final, will use the intention-to-treat principle. The baseline characteristics comparing randomized groups will be reported using means (and standard deviations), medians (and interquartile ranges) or proportions. Trial data will be analyzed using Bayesian hierarchical generalized linear models to estimate the posterior probability of superiority (or inferiority) and equivalence for each intervention within each domain. The hierarchical model will account for centre, time period, sex and oxygen support at the time of randomization (HNFC, NIV, invasive mechanical ventilation or ECLS). Posterior probability distributions will be computed by combining the likelihood function with minimally informative priors and updated every three months as information (observations) accumulate in the trial. Statistical analysis will be adjusted for whether a patient was enrolled in one CORT-E cohort or both CORT-E cohorts. We do not expect interaction between CORT-E and the other PRACTICAL domains. The final study analysis, separate for each cohort, will be completed once either superiority, inferiority or equivalence has been observed and confirmed by the DSMB and Platform Steering Committee.

We will collect sex and perform subgroup analysis based on this variable. It is less feasible to collect gender as most patients will not be conscious at the time of enrolment. We don't expect effect modification for either cohort based on sex or gender. Understanding the CORT-E eligibility criteria, we plan to enroll a diverse population of patients representative of the demographics of ICU patients presenting at the participating sites.

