As above, in keeping with the Bayesian framework, frequent reassessments of posterior distribution will occur. We plan to perform these analyses after each 200 patients have been randomized (after we have primary outcome data for each 200 patients). We will not start these interim analyses until at least 750 patients have been enrolled (again, until we have outcome data for at least 750 patients) in each domain in order to decrease the likelihood of spurious early findings based on an insufficient number of observations. These analyses will remain blinded to all study investigators and will be reviewed only by the DSMB. If stopping criteria are met, the DSMB may suggest stopping enrolment to one or both cohorts. The stopping criteria are intentionally conservative to avoid inappropriately stopping the trial early.

Six subgroups apply to both cohorts: 1) patients < 65 versus  $\geq$  65 years (hypothesizing that younger patients will benefit more from early and extended corticosteroids); 2) patients requiring HFNC or NIV versus invasive mechanical ventilation at the time of randomization (hypothesizing that patients receiving invasive ventilation will benefit more from early and extended corticosteroids); 3) male vs. female sex (hypothesizing no difference); 4) those requiring ECLS at baseline versus not requiring ECLS (hypothesizing that those requiring ECLS will benefit more

from early and extended corticosteroids; and 5) patients requiring versus not requiring vasopressor support at randomization (hypothesizing that those requiring vasopressor support will benefit more from early and extended corticosteroids). Two subgroups will apply exclusively to Extended Cohort 1) patients with COVID versus those with non-COVID AHRF (hypothesizing that those with COVID will benefit more from extended corticosteroids), 2) patients enrolled only in Extended Cohort versus those enrolled in both Early Cohort and Extended Cohort (to assess for interaction between cohorts). We will collect plasma samples at baseline to allow for post-hoc subgroup analysis for Early Cohort and Extended Cohort based on inflammatory groups (hypothesizing that those with elevated inflammatory markers [IL-6, sTNFr1 and IL-8] will benefit more from corticosteroids). We will perform these subgroup analyses only for the primary outcome.

[figure not shown]

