### **Randomization Scheme**

We will randomize using an online centralized password-protected randomization system (REDCap) following a 1:1 schedule, stratified by study site and level of oxygen support (noninvasive, invasive or ECLS) at the time of randomization.

[figure not shown]

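### The age subgroup splits patients at 65 without giving a reason; if benefit changes gradually with age, this discards about a quarter to a half of the information on the treatment-by-age interaction

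*Protocol*

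**What the plan says.** The Analyses section lists age first among the subgroups for both cohorts: "Six subgroups apply to both cohorts: 1) patients < 65 versus" 65 and over, "hypothesizing that younger patients will benefit more from early and extended corticosteroids". The subgroup work is confined to 60-day mortality: "We will perform these subgroup analyses only for the primary outcome".

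Age is collected at baseline. A footnote to the Study Assessment Schema reads "Demographics include age, gender, height, and weight". Adults from 18 upward are eligible.

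Age is not among the listed covariates of the main model: "The hierarchical model will account for centre, time period, sex and oxygen support at the time of randomization". The protocol nowhere plans age as a continuous modifier, gives no reason for a threshold at 65, and states no age distribution and no power or precision for any subgroup.

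**The concern.** Age is the only named subgroup made by cutting a measured quantity; the others (respiratory support, sex, ECLS, vasopressors, COVID status, cohort membership) are categories already. The cut treats patients aged 30 and 64 as alike and patients aged 64 and 66 as different. If benefit declines steadily with age, the two-group contrast uses only part of what the recorded ages say about that decline.

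What is at stake is precision. An interaction on mortality is hard to estimate at this sample size, and the split makes a real age gradient harder to see when the data to estimate it directly will already be in hand.

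**Working it through.** The plan states no figure on this point to reproduce. The Sample Size section's claim, "This provides a power of 94% for an" OR of 0.75, concerns the main treatment effect and is not used here.

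**Inputs from the protocol.** The cut is at 65. Allocation is 1:1 ("following a 1:1 schedule, stratified by study site and level of oxygen support"). The maximum is 2000 patients per cohort ("It is estimated that a maximum of 2000 patients will be enrolled in each cohort at 30 to 40 sites"). Interim analyses start once 750 patients have outcome data. Mortality of 20% to 50% appears in The Problem to be Addressed.

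**Assumptions.** The mean, SD and shape of the age distribution, the size of the interaction, and linearity on the log-odds scale.

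**Step 1: information kept by the cut.** Under a linear interaction this is the squared correlation between age and the indicator age ≥ 65. For normal age, with c = (65 − mean)/SD and P = Φ(c):

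kept = φ(c)² / [P(1 − P)]

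- Mean 65: c = 0, so 0.3989²/0.25 = 0.637 (that is, 2/π, the maximum). Lost: 36%.
- Mean 62, SD 15: c = 0.2, so 0.391²/0.2437 = 0.627. Lost: 37%.
- Mean 60, SD 15: kept 0.611. Lost: 39%.
- Mean 55, SD 15: kept 0.541. Lost: 46%.
- Mean 55, SD 12: kept 0.492. Lost: 51%.

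**Step 2: other age shapes, same squared correlation.**

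- Normal truncated to 18–95 years: 34.5% to 38% lost.
- Left-skewed, mean about 62, SD 15–17: 31% to 32.5% lost.
- Uniform 18–90: 32% lost.
- Uniform 40–90: 25% lost.

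The overall range is therefore about 25% to 51%. If the effect is a true step at 65, the indicator is the correct form and nothing is lost.

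**Step 3: simulation check.** Logistic models were fitted to 2000 patients allocated 1:1, with age normal (mean 62, SD 15) and an interaction of 0.25 log-odds per SD, over 1,500 runs. Mean z was 2.314 with continuous age and 1.859 with the cut. The ratio (1.859/2.314)² = 0.646 is close to the 0.627 from the formula.

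**Step 4: meaning in patients.** With 0.637 kept, 2000 patients carry the interaction information of 2000 × 0.637 ≈ 1,273. Matching the continuous analysis would take 2000/0.637 ≈ 3,140.

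**Step 5: meaning in power.** The yardstick is a one-sided 2.5% test, which under near-flat priors corresponds to a 97.5% posterior probability that the gradient runs in the hypothesised direction. The protocol sets no such threshold.

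Power with the cut = Φ[(z_power + 1.96)·√kept − 1.96]. For 80% power on continuous age this is (0.842 + 1.96) × 0.798 − 1.96 = 0.275, so power falls to 61%. A test with 90% power falls to 73%.

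Absolute power depends on mortality p and on n. For standardised age and 1:1 allocation, SE ≈ 2/√(n·p(1 − p)). With an interaction OR of 1.3 per SD (log 0.262) and kept = 0.637:

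| n | p | SE | z, continuous | Power, continuous | Power, cut |
|---|---|---|---|---|---|
| 2000 | 20% | 0.112 | 2.35 | 65% | 47% |
| 2000 | 50% | 0.089 | 2.93 | 83% | 65% |
| 750 | 20% | 0.183 | 1.44 | 30% | 21% |
| 750 | 50% | 0.146 | 1.80 | 43% | 30% |

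An OR of 1.3 per SD is a strong gradient. With an SD of 15 years, the treatment odds ratio at 75 would be 1.3² = 1.69 times that at 45. At 1.1 per SD (log 0.095), 2000 patients give only 13% to 19% with continuous age and 10% to 13% with the cut.

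**The case against.** A prespecified two-group split with a stated direction is coherent and common, and nothing in the protocol is contradicted. The hypothesis follows directly after the two groups, so it can be read as a statement about those groups and need not be a gradient. The section fixes the groups but does not exclude a continuous-age analysis, and the Synopsis refers further detail to the Master SAP, which is not available here. All of this stands. It makes the point an improvement rather than an error. It does not supply a reason for 65, and the cut is the only age comparison the protocol specifies.

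Three stronger readings are tempting, and the documents do not support them:

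- A reader might infer that this trial will lose more than a third of its interaction information. That needs near-normal age and a linear interaction, and the protocol gives neither. Several plausible age shapes fall below a third.
- A reader might infer that the trial will wrongly report a uniform effect. An imprecise interaction is not a claim of uniformity, and the protocol commits to no such reading.
- A reader might take one power figure as settled. Power moves with baseline mortality and with when the cohort stops; 2000 is a maximum. For modest gradients neither analysis would detect much.

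It would also be wrong to put the age interaction into the primary model. Age is not among its listed covariates, and that model feeds the stopping triggers.

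**Conclusion.** The point holds as an inexpensive improvement to one secondary analysis. The protocol addresses the age question with an unexplained cut at 65 although age is recorded. Under a graded effect, the cut costs about a quarter to a half of the interaction information: 36% or more for normal age with a linear log-odds interaction, and 25% to 51% across the shapes tried. There is no loss if the effect steps at 65, but the protocol argues for no such step. The age distribution and effect shape are assumptions. The relative loss does not depend on mortality or sample size to the accuracy used here, whereas absolute power depends on both. The primary analysis, stopping triggers and sample size are untouched.

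**What to change.** Define subgroup 1 as the treatment-by-age interaction on 60-day mortality with age continuous: linear, with a restricted cubic spline as a check. Fit it in a separate subgroup model that takes the covariates listed in the Analyses section and adds an age main effect, leaving the primary model and its triggers as they are. Report the posterior treatment effect with credible intervals at chosen ages, and the posterior probability that benefit is greater at younger ages. Keep the split at 65 as a display only.

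The cost is a wording change in the protocol and SAP, slightly more analysis work, and a curve beside the two-row table. No new data or patients are needed. It is best done before the analysis, because the Analyses section requires later departures from the statistical plan to be described in the final report.

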## Why This Study Is Needed

This clinical trial is designed to inform clinical practice and address two knowledge gaps in COVID and non-COVID respiratory failure.

**Early Cohort** – *There is uncertainty whether lessons learned from corticosteroids in COVID AHRF are generalizable to non-COVID AHRF.* The DEXA-ARDS trial randomized 277 critically ill patients with non-COVID ARDS to receive dexamethasone 20mg daily or placebo and found a reduction in mortality (-15.3%, 95% CI -4.9 to -25.9%) and an increase in ventilator-free days at 28 days (MD 4.8 days more, 95% CI 2.57 to 7.03 days more) with dexamethasone. A 2015 meta-analysis suggested that corticosteroids reduced mortality in patients with severe community-acquired pneumonia (RR 0.67, 95% CI 0.45 to 1.01). Despite these data suggesting benefit of corticosteroids in non-COVID AHRF, use of this therapy remains highly variable. The 2017 Society of Critical Care Medicine (SCCM) guidelines made a conditional recommendation for corticosteroids in both ARDS and CAP based on moderate certainty evidence, with a rationale that further high quality data was needed before a strong recommendation could be made.

***Patients with non-COVID AHRF, not meeting traditional ARDS criteria, but receiving HFNC or NIV may benefit from corticosteroids but have not been sufficiently studied.*** Use of HFNC has increased markedly in patients with AHRF. In fact, the most recent 2020 European guideline made a strong recommendation for HFNC in patients with AHRF. We are aware of planned updates to the ARDS definition that will include patients on HFNC. Studies evaluating the effect of corticosteroids in critically ill COVID patients demonstrated a trend towards greater effect of corticosteroids in those requiring HFNC or NIV compared to invasive mechanical ventilation (ratio of ORs 4.34, 95% CI 1.46 to 12.91) with the hypothesis that modulating the inflammatory response early before it becomes too severe may be optimal. Corticosteroids also reduce the need for invasive mechanical ventilation in patients with COVID AHRF (25 fewer per 1000, 95% CI 1 to 44 fewer). It is unclear whether these lessons learned from COVID AHRF are generalizable to non-COVID AHRF patients on HFNC or NIV.

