### Patient Population

The CORT-E trial is a phase III, multi-centre (30-40 centres), randomized, open-label trial, embedded as a domain within the PRACTICAL platform trial. This domain will enrol patients in the following platform defined states (in both trial cohorts);

[figure not shown]
- Non-intubated patients;
- Intubated patients, not on extracorporeal life support, with low normalized respiratory system elastance (<2.5 cm H2O/ml/kg predicted body weight);
- Intubated patients, not on extracorporeal life support, with high normalized respiratory system elastance (≥2.5 cm H2O/ml/kg predicted body weight);
- Patients on extracorporeal life support.

Patients who satisfy the PRACTICAL platform eligibility criteria **and** the criteria specific to **either** cohort in the CORT-E domain will be considered.

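### The ECLS subgroup is compared with a mix of non-invasive and invasively ventilated patients, so a difference it shows could not be attributed to ECLS rather than to ventilation mode

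*Protocol*

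**What the plan says.** Two of the subgroups that the protocol's Analyses section applies to both cohorts concern respiratory support at baseline.

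- The second compares "patients requiring HFNC or NIV versus invasive mechanical ventilation at the time of randomization". The expectation attached to this comparison is worded as "hypothesizing that patients receiving invasive ventilation will benefit more from early and extended corticosteroids".
- The fourth compares "those requiring ECLS at baseline versus not requiring ECLS". Here the attached expectation points the same way, towards the more invasive support: "hypothesizing that those requiring ECLS will benefit more".

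Elsewhere the protocol treats ECLS as a level of its own. Randomization is "stratified by study site and level of oxygen support (noninvasive, invasive or ECLS) at the time of randomization" (Randomization Scheme; Patient Randomization agrees). The platform states under Patient Population list "Non-intubated patients", two groups of intubated patients not on ECLS, and patients on ECLS. The daily respiratory support scale under Secondary Outcomes also gives ECLS and invasive ventilation separate categories.

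The hierarchical model in Analyses is to account for "oxygen support at the time of randomization (HNFC, NIV, invasive mechanical ventilation or ECLS", among other factors. No treatment-by-support term is named there, and nothing says that the second and fourth subgroups will be estimated together.

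**The concern.** The group not on ECLS contains both non-intubated and intubated patients, and the second subgroup expects corticosteroids to work differently in these two. The fourth subgroup therefore takes as its reference an average of two effects that the plan itself predicts to be unequal, weighted by whatever mix is enrolled. If ECLS patients respond much as other invasively ventilated patients do, the fourth subgroup will still show a difference whenever the second does.

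Adjusting for support level as a main effect does not remove this. Such a term absorbs differences in baseline mortality between levels, not differences in treatment effect.

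At stake is interpretation. Both hypotheses point the same way, towards more benefit with more invasive support, so one ventilation effect could be read as two confirmed predictions. If the effect ran the other way, the ECLS result would tend to contradict its hypothesis even if ECLS itself modified nothing.

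**Working it through.** The protocol states no effect size, power or sample size for any subgroup, so there is no figure of the plan to reproduce.

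**Inputs from the protocol.** About 2000 patients per cohort at most (Sample Size); 1:1 allocation (Randomization Scheme); mortality between 20% and 50% depending on severity (The Problem to be Addressed).

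**Assumptions, because the protocol gives no values.** 5% of patients on ECLS (100 of 2000); 30%, 50% or 60% of all patients non-invasive, the rest invasive without ECLS; mortality 30% non-invasive, 40% invasive, 50% ECLS. The treatment odds ratio (OR) is 0.90 in non-invasive patients and 0.70 in both invasive and ECLS patients. This follows the hypothesised direction and sets the true ECLS-versus-invasive ratio of ORs to 1.0.

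**Step 1: effect in the pooled comparator.** Information is proportional to n·p·(1−p), with p(1−p) = 0.3 × 0.7 = 0.21 non-invasive and 0.4 × 0.6 = 0.24 invasive. For a non-invasive share s, the non-invasive weight is

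w = 0.21·s / [0.21·s + 0.24·(0.95 − s)].

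The pooled log OR is w·ln 0.90 + (1 − w)·ln 0.70. The apparent ECLS ratio of ORs is 0.70 divided by the pooled OR.

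| Non-invasive share | w | Pooled OR | Apparent ratio | Log shift |
|---|---|---|---|---|
| 30% | 0.288 | 0.752 | 0.93 | −0.07 |
| 50% | 0.493 | 0.792 | 0.88 | −0.12 |
| 60% | 0.600 | 0.814 | 0.86 | −0.15 |

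**Step 2: noise.** The variance of a log OR in a group of n patients allocated 1:1 is about 4/[n·p·(1−p)].

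- ECLS: 4/(100 × 0.25) = 0.160, so SE 0.40.
- About 1900 patients not on ECLS, average p(1−p) about 0.225: 4/(1900 × 0.225) = 0.0094.
- SE of the ECLS-versus-rest contrast: √(0.160 + 0.0094) = 0.41.

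The shift is 0.07/0.41 = 0.18 to 0.15/0.41 = 0.37 standard errors. As a yardstick only, since the protocol sets no threshold for subgroup interactions, a nominal two-sided 5% test would flag about 5.4 to 6.6% of the time.

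**Step 3: other assumptions.** A separate calculation took mortality of 25%, 40% and 50%, non-invasive shares of 30 to 70% of patients not on ECLS, an ECLS share of 2 to 10%, and ORs of 1.0 or 0.9 against 0.75 or 0.65. With no ECLS-specific effect, the apparent ratio was 0.81 to 0.96 and the flag rate 5 to 12%, the upper end from simulation. With equal effects in non-invasive and invasive patients, the ratio was 1.00 and the flag rate 5%, so the shift comes only from the ventilation interaction.

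**Step 4: the opposite direction.** Why This Study Is Needed reports a greater effect with HFNC or NIV in critically ill COVID patients ("ratio of ORs 4.34, 95% CI 1.46 to 12.91"). With the weights of Step 1 the apparent ECLS ratio is (ratio of ORs)^w. This gives about 1.1 to 1.3 at the lower limit of 1.46, and 4.34^0.288 = 1.5 to 4.34^0.600 = 2.4 at the point estimate. Under the assumptions of Step 3, the point estimate gives 1.3 to 2.2, with flag rates of about 10 to 70%.

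**Step 5: the alternative contrast.** With a treatment-by-HFNC/NIV term added, so that ECLS is compared only with invasively ventilated patients, the simulated median ratio was 0.96 to 1.04 and the flag rate about 3 to 7%. For precision, take about 950 invasive patients: 4/(950 × 0.24) = 0.0175, and √(0.160 + 0.0175) = 0.42. That is about 2.4% above 0.41 (unrounded, 0.421 against 0.411).

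**The case against.** The strongest reply is that the contrast matches the hypothesis. The protocol predicts more benefit in patients on ECLS and compares them with those who are not. It does not ask what ECLS adds beyond invasive ventilation, and every one-factor subgroup has a mixed comparator. This stands to the extent that the ECLS-versus-rest difference would be real. A reader might infer that the plan can produce a false interaction. The protocol does not support that: only attribution to ECLS is unsafe. What distinguishes this subgroup from the others is that the factor mixed into its comparator is one whose interaction the same list predicts, and the strata that would separate the two are already recorded.

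A reader might also infer that ventilated ECLS patients are counted in both subgroups. The wording of the second subgroup does not say where they go. But the strata, the platform states, the model covariate and the ordinal scale all treat ECLS as its own level, so the natural reading leaves them out.

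The ratios of 1.5 to 2.4 are tempting as the headline size. They rest on an estimate in COVID patients with a wide interval, which the protocol itself says may not carry over to non-COVID patients. The Early Cohort excludes confirmed or strongly suspected COVID, so that magnitude cannot be claimed for both cohorts.

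Finally, joint modelling could be set out in the SAP, which is not at hand. That is fair, but the contrast itself is fixed in the protocol.

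**Conclusion.** The point holds as an improvement to the subgroup plan, not as an error. As worded, the fourth subgroup cannot separate an ECLS effect from a ventilation effect, and its result would not be evidence independent of the second subgroup.

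In the hypothesised direction the size is modest: an apparent ratio of ORs of about 0.86 to 0.93 where the ECLS-versus-invasive ratio is 1.0, at most about 0.37 standard errors. It is larger only if the ventilation interaction is large, and it vanishes if there is none.

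These figures rest on assumed ECLS and non-invasive shares and mortality by support level. They also assume that ECLS patients respond like invasively ventilated ones. If some ECLS patients are not intubated and respond like non-invasive patients, the shift is smaller and the alternative contrast is itself somewhat mixed. The primary comparison and the stopping triggers are untouched. Severity is low.

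**What to change.** Replace the second and fourth subgroups with one analysis of the three-level randomization stratum: non-invasive; invasive without ECLS; ECLS. Assign each patient to one level as recorded at randomization. Add a treatment-by-stratum term to the hierarchical model already planned and report two contrasts: invasive versus non-invasive, and ECLS versus invasive without ECLS. State the ECLS hypothesis against the latter comparator. The ECLS-versus-all-others contrast may stay as a descriptive summary, with a note that it reflects ventilation mode as well.

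The cost is wording in the protocol and the matching SAP text, with no new data or patients. The ECLS contrast loses a little precision because its comparator is smaller: its standard error rises by about 2 to 3% (0.41 to 0.42) when the patients not on ECLS divide about evenly between non-invasive and invasive. The small ECLS group dominates the variance either way.
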